7.3 Secondary Analyses

7.3.1 Time to Diagnosis

Statistical Method: Friedman test (a non-parametric test for repeated measures across multiple groups) followed by a Wilcoxon signed-rank test.

Rationale: The Friedman test is appropriate because:

- **Within-reader design:** Each reader reviews slides under all three conditions, creating paired data at the reader level
- **Non-parametric approach:** Does not assume normal distribution of review times
- **Accounts for reader variability:** Controls for baseline differences among readers by treating each reader as a block
- **Appropriate for repeated measures:** Tests within-reader differences across conditions

Analysis Procedure:

1. **Data aggregation:** For each reader and condition, calculate the median review time across all slides reviewed in that condition (reader-level aggregation: $n = 10$ readers \times 3 conditions = 30 observations total).
2. **Outlier detection:** Prior to aggregation, identify and remove extreme outlier values at the slide level using the 3-sigma rule (values exceeding mean \pm 3 standard deviations within each condition). The large outliers likely represent cases where participants left the computer with the slide review running. Analyses will be conducted both with and without the detected outliers.
3. **Global test:** Conduct a Friedman test with the null hypothesis that the distributions of the time are identical across all conditions.
4. **Significance threshold:** Two-sided alpha = 0.05.
5. **Post-hoc pairwise comparisons:** If the Friedman test yields $p < 0.05$, conduct pairwise Wilcoxon signed-rank tests for all condition pairs.

Wilcoxon Signed-Rank Test Rationale: This paired non-parametric test is appropriate for two-sample comparisons because it preserves the within-reader pairing structure (each reader's median review time is compared between conditions of interest) and does not assume normality of the differences between conditions.

7.3.2 Inter-Observer Variability

Statistical Method:

- Cohen's kappa will be calculated to assess overall inter-rater agreement.

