1.8 Secondary Objectives

- To assess the time required to reach a diagnosis under different conditions
- To measure inter-observer variability across conditions
- To determine concordance between AI predictions and clinicians' diagnoses

- To evaluate decision-change rates after clinicians reviewed AI diagnostic results
- To quantify the net benefit of AI assistance on diagnostic accuracy
- To assess clinician confidence levels across conditions

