2.2 Secondary Objectives

1. **Time efficiency:** To assess the average time required to reach a diagnostic decision under each condition.
2. **Inter-observer agreement:** To measure the consistency of diagnoses among clinicians across different conditions using inter-rater reliability metrics.
3. **AI-clinician concordance:** To determine the proportion of cases where AI predictions match clinicians' final diagnoses in each condition.
4. **Decision revision patterns:** To quantify how often clinicians change their initial diagnosis after viewing AI predictions in the "AI as Double-Check" condition.
5. **Net diagnostic benefit:** To calculate the overall improvement in diagnostic accuracy attributable to AI assistance.
6. **Confidence assessment:** To evaluate clinicians' self-reported diagnostic confidence across conditions and examine the relationship between confidence and accuracy.

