5.3 Study Completion

Actual Study Start Date: September 9, 2025

Actual Study Completion Date: October 10, 2025

Actual Number of Participants: 10

Actual Number of Slides per Participant: 102 (34/34/34)

Actual Number of Total Diagnostic Decisions in This Study: 1,020

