6.2.2 Inter-Observer Variability

Measurement Time Frame: Periprocedural (at the time of slide review)

Description: Agreement among clinicians across the three conditions, measured using inter-rater reliability metrics:

- Cohen's kappa (for pairwise agreement)

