7.1.2 Level of Significance

A two-sided alpha level of 0.05 will be used for all comparisons.

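### Reader agreement is a secondary outcome across the three conditions, but SAP 7.3.2 specifies only an overall kappa, with no per-condition estimate, interval or between-condition contrast

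*Combined protocol and SAP*

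**What the plan says.** The outcome is described by condition in three places. Section 1.8 lists the objective "To measure inter-observer variability across conditions". Section 2.2 gives it as "To measure the consistency of diagnoses among clinicians across different conditions using inter-rater reliability metrics". Section 6.2.2 defines the outcome as "Agreement among clinicians across the three conditions, measured using inter-rater reliability metrics" and names pairwise Cohen's kappa as the only metric.

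The method in 7.3.2 is a single bullet: "Cohen's kappa will be calculated to assess overall inter-rater agreement". Section 7.1.2 adds that "A two-sided alpha level of 0.05 will be used for all comparisons", but no comparison of kappas is defined anywhere for that level to apply to.

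Section 3.4 divides the 102 slides into three sets of 34 separately for each reader, stratified by APL status. Section 5.3 reports 10 readers and 34 slides per reader in each condition.

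**The concern.** The analysis section does not carry through the outcome that the objectives define. It leaves four things open: whether kappa is calculated per condition, how the reader pairs are combined into one figure, whether the pre-AI or post-AI diagnosis counts in Y1, and how uncertainty is expressed. No other section settles any of them.

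The outcomes nearest in kind are fully specified. Performance (7.2.1) and time (7.3.1) have a Friedman test followed by Wilcoxon tests, and concordance with the AI (7.3.3) has pairwise permutation tests between conditions.

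What is at stake is the claim that LEAP makes clinicians more consistent. A higher kappa with AI than without is easily read that way, and nothing in the plan would show whether the gap is larger than chance produces with 10 readers and 34 slides per reader and condition.

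**Working it through.** **1. The plan's own figure.** Section 5.3 gives 1,020 decisions. 10 readers × 102 slides = 1,020, and 3 × 34 = 102, so the figure reproduces. The documents state no expected kappa and no precision for kappa.

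**2. Information behind each kappa.** Cohen's kappa is (p_o − p_e) / (1 − p_e), where p_o is observed agreement and p_e is agreement expected by chance. It can only be calculated on slides that both readers saw in the same condition.
- Reader pairs: 10 × 9 / 2 = 45.
- Expected shared slides per pair and condition: 34 × 34 / 102 = 11.3. The central 95% range is 7 to 16 (hypergeometric, ignoring the stratification, which does not change the mean if each stratum is split in thirds).

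This step uses only the documents' figures. The 45 pairs also overlap in readers and slides, so they are not 45 independent pieces of evidence.

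**3. Size of chance differences.** The documents do not give the number of APL slides, reader accuracy or slide difficulty, so these are assumptions:
- 18, 33 or 51 APL slides of 102;
- sensitivity = specificity = 0.80, 0.90 or 0.95, the same for all readers;
- slide-difficulty SD of 1 or 0 on the probit scale.

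Reader diagnoses were simulated with no effect of condition and allocated as in 3.4. Mean pairwise kappa was calculated per condition and two conditions were compared (400 runs per row):

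| APL slides | Accuracy | Difficulty SD | Mean pairwise kappa | SD of difference | 95th percentile of absolute difference |
|---|---|---|---|---|---|
| 18 | 0.80 | 1 | 0.45 | 0.098 | 0.178 |
| 18 | 0.90 | 1 | 0.61 | 0.098 | 0.193 |
| 18 | 0.95 | 1 | 0.76 | 0.093 | 0.187 |
| 33 | 0.80 | 1 | 0.51 | 0.093 | 0.184 |
| 33 | 0.90 | 1 | 0.69 | 0.085 | 0.169 |
| 33 | 0.95 | 1 | 0.82 | 0.076 | 0.146 |
| 51 | 0.80 | 1 | 0.53 | 0.086 | 0.168 |
| 51 | 0.90 | 1 | 0.72 | 0.081 | 0.165 |
| 51 | 0.95 | 1 | 0.84 | 0.064 | 0.127 |
| 33 | 0.90 | 0 | 0.60 | 0.083 | 0.165 |

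A single pair's kappa has an SD of about 0.17 to 0.30 in these runs.

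A separate simulation of the same grid, with both difficulty settings throughout, gave an SD of 0.06 to 0.105 for Y2 − X. The absolute difference exceeded 0.10 in about 8% to 38% of studies. The outer ends of that range include Monte Carlo error: a longer repeat (4,000 runs per scenario) gave SDs of 0.063 to 0.103 and exceedance in 12% to 33%.

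**4. What an interval would look like.** 1.96 × 0.06 = 0.12 and 1.96 × 0.105 = 0.21, so a 95% interval for a difference between two conditions would run roughly ±0.12 to ±0.21.

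**The case against.** The strongest reply is that 7.3.2 should not be read so harshly. A reader might infer that the SAP yields one kappa pooled over all conditions. The text does not say so. Section 7.3.3 uses the word overall for a concordance rate calculated within each condition, and 6.2.2 points towards kappas by condition. That stands: the SAP does not exclude per-condition values, it just does not specify them.

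A reader might also infer that the plan commits to a formal comparison of agreement. The objectives say measure, whereas 6.2.1 (time) and 6.2.6 (confidence) say compare. A descriptive secondary outcome is legitimate, so a p-value is optional. An interval is harder to do without if conditions are set side by side.

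Nor is kappa the only gap. Net benefit (6.2.5) has no analysis subsection, and no analysis in section 7 specifies a confidence interval.

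Finally, the simulated frequencies depend on assumptions. Large chance differences become less common when accuracy is very high, and the 0.10 threshold is only a yardstick. This limits the precision of the size given, but it does not supply the missing estimate, interval or contrast.

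**Conclusion.** The gap is real and affects a secondary outcome. An outcome defined across three conditions has an analysis that names none of them and gives no measure of error. On one reading of 7.3.2 the objective goes unanswered; on the other it is answered by point estimates alone.

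The 11.3 shared slides per reader pair and condition follow from the design. The chance SD of about 0.06 to 0.105, and the roughly 8% to 38% of null studies with a difference above 0.10, rest on assumed APL counts of 18 to 51, accuracy of 80% to 95% and identical readers.

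The documents do not support going further and saying that an observed difference in kappa would probably be chance. No results are given, and in every scenario examined most null studies show a difference between two given conditions of 0.10 or less. The supported conclusion is that the plan as written could not tell the two apart.

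**What to change.** In 7.3.2:
- Calculate the agreement coefficient separately for X, Y1 (final, post-AI diagnosis) and Y2, and state how the 45 reader pairs are combined.
- Report Y1 − X, Y2 − X and Y2 − Y1 with 95% intervals from a bootstrap over slides and readers. Exclude pairs formed by a reader and its own resampled duplicate: they agree perfectly and inflate kappa. In one check (34 APL slides, 85% accuracy), mean kappa rose from 0.61 to 0.65 when they were kept.
- If a p-value is wanted, obtain it by re-randomising slides to conditions within reader and APL status, which matches the allocation in 3.4 and 5.1.2.
- Label the analysis as specified after data collection, since sections 10.2 and 10.3 show the study complete under version 1.0 without amendment.
- Claim no change in consistency from point estimates alone.

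The cost is a few lines of SAP text and a short script. No new data are needed. The downside for the sponsor is that an apparent gain in kappa may prove to be within chance.

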7.3.3 Concordance Between AI Predictions and Clinicians' Diagnoses

Statistical Method: Permutation tests comparing AI predictions to clinician decisions.

Rationale:

- **Distribution-free:** Avoids large-sample and normality assumptions by creating an empirical null distribution through random permutations
- **Appropriate for proportion comparison:** Tests whether the proportion of cases where clinicians agree with AI differs significantly between conditions
- **Robust to small samples:** Does not rely on asymptotic approximations
- **Exact p-values:** Provides exact statistical inference rather than relying on theoretical distributions
- **Slide-level analysis:** Treats each clinician's diagnosis on each slide as an independent observation when comparing concordance rates between conditions

Analysis Procedure:

1. For each condition and each slide, determine the AI prediction (APL vs. non-APL).
2. For each clinician's diagnosis, determine whether it matches the AI prediction (concordant vs. discordant).
3. Calculate the overall concordance rate for each condition: proportion of all clinician-slide pairs where the diagnosis matches the AI prediction.
4. Conduct pairwise permutation tests comparing concordance rates between conditions:
 - Calculate the observed difference in concordance rates between two conditions
 - Randomly permute condition assignments while preserving the total number of observations per condition
 - Recalculate the difference in concordance rates for each permutation ($n=10,000$ permutations)
 - Compute two-sided p-value as the proportion of permuted differences as extreme or more extreme than the observed difference

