6.2.3 Concordance Between AI Predictions and Clinicians' Diagnoses

Measurement Time Frame: Periprocedural (at the time of slide review)

Description: The proportion of cases in which AI predictions match clinicians' final diagnoses in each study condition. This will be calculated as the percentage agreement between LEAP predictions and clinician diagnoses. Concordance will be evaluated separately for Conditions X, Y1, and Y2.

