7.2 Primary Analysis

7.2.1 Primary Endpoint Analysis

Objective: To compare diagnostic performance (accuracy, sensitivity, specificity, PPV, NPV) across the three study conditions.

Diagnostic Performance Metrics:

For each reader and condition, the following metrics will be calculated:

- **Accuracy:** Overall proportion of correct diagnoses
- **Balanced Accuracy:** Average of sensitivity and specificity, accounting for class imbalance
- **Sensitivity:** Proportion of APL cases correctly identified
- **Specificity:** Proportion of non-APL cases correctly identified
- **Positive Predictive Value (PPV):** Proportion of APL predictions that are correct
- **Negative Predictive Value (NPV):** Proportion of non-APL predictions that are correct
- **Weighted F1 Score:** Harmonic mean of precision and recall, weighted by class prevalence

Statistical Method: Friedman test (a non-parametric test for repeated measures across multiple groups) followed by a Wilcoxon signed-rank test.

Rationale: The Friedman test is the appropriate statistical method for this study design because:

- **Within-subject design:** Each reader evaluates cases under all three conditions, creating paired data
- **Non-parametric approach:** Does not assume normal distribution of performance metrics, which is appropriate for bounded proportions (0-1 range)
- **Accounts for reader variability:** Controls for baseline differences among readers by treating each reader as a block, focusing on within-reader differences across conditions
- **Multiple conditions:** Simultaneously tests for differences among three related groups (X, Y1, Y2) rather than requiring multiple pairwise tests
- **Robust to outliers:** Uses rank-based methods that are less sensitive to extreme values

Analysis Procedure:

1. **Global test:** For each performance metric, conduct a Friedman test with the null hypothesis that the distributions of the metric are identical across all conditions.
2. **Significance threshold:** Two-sided alpha = 0.05.
3. **Post-hoc pairwise comparisons:** If the Friedman test yields $p < 0.05$ for a given metric, conduct pairwise Wilcoxon signed-rank tests for all condition pairs.

Wilcoxon Signed-Rank Test Rationale: This paired non-parametric test is appropriate for two-sample comparisons because it preserves the within-reader pairing structure and does not assume normality of the differences between conditions.

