7.3.5.2 Level-Specific Confidence Changes

Statistical Method: McNemar test for paired pathology evaluation with and without AI.

Rationale: The McNemar test is appropriate because:

- **Paired data:** Compares pre-AI and post-AI confidence for the same clinician on the same cases
- **Binary classification:** At each confidence level (1-5), each case can be classified as either at that confidence level or not
- **Focus on discordant pairs:** Tests whether changes in confidence at a specific level differ significantly between pre-AI and post-AI assessments
- **Accounts for within-subject dependence:** Properly handles the matched nature of pre- and post-AI assessments
- **No distributional assumptions:** Non-parametric test suitable for ordinal confidence ratings

Analysis Procedure:

1. For each confidence level (1 = Random Guess, 2 = Very Doubtful, 3 = Unsure, 4 = Mostly Certain, 5 = Absolutely Certain) in Condition Y1 (AI as Double-Check):

- Create binary indicators: 1 if confidence equals that level, 0 otherwise
- Construct 2×2 contingency table comparing pre-AI vs. post-AI classifications
- Conduct McNemar exact test with null hypothesis that the proportion of cases at that confidence level is unchanged by AI exposure

2. Calculate the proportion of cases at each confidence level before and after AI review
3. Compute the change in proportion (post-AI minus pre-AI) for each confidence level
4. Report both increases and decreases in confidence at each level following AI review.

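### Section 7.3.3 tests concordance in three pairwise comparisons without the global gate used in 7.2.1 and 7.3.1, and its permutation p-value can equal 0

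*Combined protocol and SAP*

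**What the plan says.** Protocol section 6.2.3 makes concordance a secondary outcome and states: "Concordance will be evaluated separately for Conditions X, Y1, and Y2". SAP section 7.3.3 then sets the test: "Conduct pairwise permutation tests comparing concordance rates between conditions". Three conditions give three pairs. The section has no preceding global test and no multiplicity adjustment, and section 7.1.2 applies one threshold throughout: "A two-sided alpha level of 0.05 will be used for all comparisons".

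Section 7.2.1 handles the same three conditions differently. Only when the Friedman test for a metric gives p < 0.05 does the plan "conduct pairwise Wilcoxon signed-rank tests for all condition pairs". Section 7.3.1 repeats that gate for time to diagnosis.

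The p-value rule in 7.3.3, applied to 10,000 random permutations, is: "Compute two-sided p-value as the proportion of permuted differences as extreme or more extreme than the observed difference". Among its reasons for choosing the method, the section says that it "Provides exact statistical inference rather than relying on theoretical distributions".

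**The concern.** With three conditions, a valid global test at 0.05 followed by pairwise tests at 0.05 is a closed procedure. If all three conditions are equal, the global test limits the error. If they are not all equal, at most one pairwise null can still be true, and its own test limits the error. Sections 7.2.1 and 7.3.1 have this structure. Section 7.3.3 drops it without giving a reason, so a concordance difference can be declared on weaker evidence than the same contrast needs elsewhere in the SAP.

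The p-value rule is a separate matter. When the observed arrangement is left out of the count, the rule returns 0 whenever no sampled permutation reaches the observed difference. A p-value of 0 cannot be correct, because the observed arrangement is itself one of the possible permutations. It also contradicts the section's claim of exactness.

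**Working it through.** **Inputs from the documents.** 10 readers with 102 slides each, 34 per condition (sections 1.5, 4.2.1, 5.3). Two-sided 0.05 per comparison (7.1.2). 10,000 permutations, with each clinician-slide read treated as independent (7.3.3). The documents give no expected concordance, so 70% to 98% is an assumed range.

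**The plan's own figure.** 10 × 102 = 1,020 decisions, as stated in 5.3. Per condition, 10 × 34 = 340. The plan states no familywise error rate.

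**Nominal familywise error, all three rates equal.**
- Large-sample value for all pairs of three equal groups: P(studentized range, k = 3, infinite df > 1.96 × √2) = 12.2%.
- If the tests were independent: 1 − 0.95³ = 14.3%. Bonferroni bound: 3 × 0.05 = 15%.

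**Familywise error of the test as planned.** The permutation test on 340 versus 340 binary outcomes is discrete, so each test has a true size below 5%. The table comes from simulation with independent reads and 40,000 runs per row. A three-group chi-square test at 0.05 stood in for the global permutation test.

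| True concordance | One test | Any of three, no gate | Any of three, with gate |
|---|---|---|---|
| 70% | 4.2% | 10.3% | 4.9% |
| 80% | 4.1% | 10.3% | 5.3% |
| 85% | 4.1% | 10.0% | 5.1% |
| 90% | 3.7% | 9.5% | 5.0% |
| 95% | 3.3% | 8.2% | 4.9% |
| 98% | 2.5% | 6.3% | 4.3% |

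**If only X differs.** The only true null left is Y1 versus Y2, so the error is the single-test size in the second column, which is below 5% with or without a gate. With X at 85% and Y1 = Y2 = 95%, simulated false rejection of Y1 versus Y2 is 3.1% both ways.

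**How often p = 0.** Let b be the number of the 10,000 permuted differences at least as extreme as the observed one. The planned p is b/10,000. Given the full permutation p-value, P(b = 0) = (1 − p)^10,000.
- Observed rates of exactly 85% and 95% (289/340 and 323/340): p = 0.0000174, and (1 − 0.0000174)^10,000 = 84%.
- Averaged over binomial sampling around assumed true rates: 85% versus 95% gives 61.5%, 80% versus 95% gives about 97%, and 90% versus 95% gives about 5%.

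**Effect on decisions.** With the criterion p < 0.05, b/10,000 rejects when b ≤ 499. The alternative (b+1)/10,001 also rejects when b ≤ 499 (500/10,001 = 0.049995) and not at b = 500 (501/10,001 = 0.0501). The decisions are the same. The smallest reportable value becomes 1/10,001, about 0.0001.

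**The case against.** Concordance is secondary, and the SAP claims no familywise control over secondary outcomes, so gating it is partly a matter of preference. The excess error also arises only if all three rates are equal. The AI output is hidden in X and shown before the final diagnosis in Y1 and Y2 (section 3.6), so X may well differ, and then the gate adds nothing. Both points stand and keep the matter small. They do not explain why the plan gates the same pairs in two other places.

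Some stronger readings are not supported:
- A reader might take the error rate to be 12%. That assumes each test has size exactly 5%, which the discrete planned test does not reach.
- A reader might infer that p = 0 would produce false findings. It would not, because the decisions are identical.
- A reader might extend the argument to section 7.3.5.2, where the instruction "Conduct McNemar exact test with null hypothesis that the proportion of cases at that confidence level is unchanged by AI exposure" is applied at five levels, and want it gated on the signed-rank test in 7.3.5.1. The three-group closure argument does not carry over to five levels. The signed-rank test also looks for a directional shift. If 40 reads moved from level 3 to 2 and 40 from 3 to 4, it would give p = 1, while McNemar's test at level 3 would give p below 1e-20. The gate would hide a change the plan intends to report. Any error rate for those five tests would also depend on how many reads change level, which the documents do not give.

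The objection that a gate does not secure 5% also stands. If condition effects vary between readers around zero (assumed logit SD 0.3 to 0.5, concordance 85% to 95%), familywise error is about 11% to 33% without the gate and still about 7% to 24% with it. That comes from treating reads as independent, which is a separate issue.

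**Conclusion.** The point holds as a minor inconsistency in a secondary analysis, together with a reporting error. Without a gate, the chance of at least one false concordance difference is about 6% to 10% rather than 5%, provided all three rates are equal, reads are independent and true concordance lies between 98% and 70%. If X alone differs, there is no excess. The p-value rule can return 0, and how often depends strongly on the assumed rates: about 5% of trials at 90% versus 95%, and about 97% at 80% versus 95%. The fault lies in the reported value and the claim of exactness. The primary analysis is not affected.

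**What to change.** In section 7.3.3, first run one permutation test of equal concordance across X, Y1 and Y2, and run the pairwise tests only if it gives p < 0.05, as 7.2.1 and 7.3.1 already do. Under independence this brings the familywise error to about 4% to 5%. Compute every permutation p-value, global and pairwise, as (b+1)/(10,000+1), and describe it as a Monte Carlo permutation p-value. Leave 7.3.5.2 ungated.

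The cost is a few sentences of SAP text and a short re-run on stored data, with slightly fewer nominally significant secondary results. Section 10.2 shows that the study is complete, so if results are already known the change should be disclosed as made afterwards. It does not resolve the treatment of reads as independent.

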3.4 Slide Allocation

For each participant, the 102 WSIs are randomly divided into three disjoint subsets (SX, SY1, SY2), each containing 34 slides. The allocation is stratified by APL status to ensure balanced representation of positive and negative cases across all three conditions.

Key principles:

- No slide is shown to the same reader more than once.
- Slide allocation is unique to each reader.
- Stratification ensures a comparable APL prevalence across all three subsets for each reader.

- Randomization minimizes bias from case difficulty or other confounders.

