5. STUDY PROCEDURES

5.1 Pre-Study Procedures

5.1.1 *AI Prediction Generation*

Prior to participant enrollment, the LEAP AI system generates diagnostic predictions for all 102 study cases. AI predictions are stored securely and revealed to participants only according to the assigned study condition.

5.1.2 *Randomization Procedures*

- Participants are randomized to Arm 1 (X→Y) or Arm 2 (Y→X) using a computer-generated randomization sequence with size 2 and size 4 blocks.
- For each participant, slides are randomly allocated to subsets SX, SY1, and SY2 with stratification by APL status
- All randomization is performed using validated software and documented in the study database.

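### The concordance permutation test ignores the reader-by-APL-status allocation, so its p-values are not the exact randomisation p-values claimed; treating reads as independent does not support claims about clinicians in general

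*Combined protocol and SAP*

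**What the plan says.** Section 5.1.2 of the combined protocol and SAP sets out the allocation: "For each participant, slides are randomly allocated to subsets SX, SY1, and SY2 with stratification by APL status". Section 3.4 adds: "Slide allocation is unique to each reader". Each reader has 34 slides in each of the three conditions.

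Section 7.3.3 tests concordance with the AI, a secondary outcome, by pairwise permutation tests. It takes each clinician's diagnosis "on each slide as an independent observation when comparing concordance rates between conditions". The shuffle is described as "Randomly permute condition assignments while preserving the total number of observations per condition", with 10,000 permutations, and the p-value rule is "Compute two-sided p-value as the proportion of permuted differences as extreme or more extreme than the observed difference". Among the reasons given for the method is this: "Provides exact statistical inference rather than relying on theoretical distributions". Section 7.1.2 sets the level: "A two-sided alpha level of 0.05 will be used for all comparisons".

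No section confines the shuffle to a reader or an APL stratum. Sections 7.2.1 and 7.3.1, by contrast, justify their tests by using the reader as the blocking factor.

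**The concern.** A randomisation test is exact when it re-draws the allocation as it was made. Here that means shuffling labels inside 20 strata (10 readers by 2 APL classes). Holding only the totals fixed admits patterns that could not have occurred, such as unequal numbers per condition within one reader or among APL slides. Differences between readers and between APL classes then widen the null distribution, although the balanced allocation has already removed them from the observed difference.

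The second issue runs the other way. The test treats 340 reads per condition as independent, but only 10 readers supply them. If the AI moves some readers towards it and others away, the sampling of readers adds variation that neither form of read-level shuffle contains. A small p-value would then be weak support for a statement about clinicians in general.

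**Working it through.** **Inputs from the documents.** 10 readers and 34 slides per condition (section 5.3); two-sided alpha 0.05 (section 7.1.2); 10,000 permutations (section 7.3.3). The number of APL slides, the spread between readers and the expected concordance are not given. Section 1.3 mentions disagreement between observers but gives no size.

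**Count.** 10 × 3 × 34 = 1,020 reads, which reproduces the total in section 5.3. That gives 10 × 34 = 340 reads per condition and 2 × 340 = 680 per pairwise test.

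**What the free shuffle allows.** A reader contributes 68 of the 680 reads, and the design fixes 34 in each condition. Under the free shuffle the reader's count in one condition is hypergeometric with mean 34 and SD √[68 × 0.25 × (612/679)] = 3.9. The chance that a given reader keeps the designed 34/34 split is C(68,34) × C(612,306) / C(680,340), about 10%.

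**Null variances.** Let K be the number of concordant reads among the 680, and let K_s be the number in stratum s, which has n_s reads per condition. For the concordant count in one condition:

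- free shuffle: 340 × (K/680) × (1 − K/680) × 340/679
- within strata: the sum over 20 strata of n_s × (K_s/2n_s) × (1 − K_s/2n_s) × n_s/(2n_s − 1)

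The second is smaller than the first when concordance differs appreciably between strata.

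**Simulation of size and power.** 4,000 trials per scenario, allocated as in sections 3.4 and 5.1.2, with the exact null distribution for each test. Assumptions: slide SD 1 logit; baseline 2 logits (2.5 in the last row); a constant AI effect of +0.6 logit for power. Where two figures are separated by a slash, they are for 10 and 17 APL slides per condition.

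| Reader SD, APL gap (logits) | Variance ratio, stratified/free | Rejection with no effect: free | stratified | Power: free | stratified |
|---|---|---|---|---|---|
| 0, 0 | 1.00 / 1.00 | 3.7% / 4.1% | 3.6% / 4.1% | 59.8% / 58.5% | 59.6% / 58.3% |
| 0.5, 0.5 | 0.97 / 0.97 | 3.9% / 4.0% | 4.1% / 4.3% | 61.5% / 64.5% | 62.4% / 65.5% |
| 0.5, 1.5 | 0.91 / 0.90 | 3.0% / 3.3% | 4.0% / 4.2% | 66.2% / 70.4% | 69.4% / 73.5% |
| 1, 1.5 | 0.85 / 0.84 | 2.9% / 2.3% | 4.1% / 3.5% | 63.5% / 66.3% | 69.3% / 72.7% |
| 1, 3 | 0.70 / 0.69 | 1.5% / 1.5% | 3.9% / 4.0% | 48.1% / 56.7% | 64.1% / 70.8% |

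Simulation error is about 0.3 points for rejection with no effect and 0.8 points for power. The power lost is about 0, 1, 3, 6 and 14-16 points down the table. At a smaller effect of +0.45 logit, with reader SD 1 and APL gap 1.5, power was 39% free and 46% stratified, a loss of 7 points.

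**Reader-varying response.** Here the AI effect averages zero on the logit scale and varies between readers (reader SD 1, APL gap 1.5).

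- Response SD 0.6: read-level permutation rejects about 9-13%.
- Response SD 1.0: about 19-26%.
- In each case the stratified form lies at the upper end, and the sign-flip test on the 10 within-reader differences stays near 4%.

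Part of the excess is a real shift, because effects centred on the logit scale lower mean concordance (0.4 to 1.6 points at a response SD of 0.7 in the scenarios of the table). With effects centred near zero on the probability scale (mean shift under 0.5 points), rejection over the same range of SDs was still 10-19% free and 13-23% stratified, against 4% for sign-flip.

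**P-value rule.** With b permuted differences as extreme as the observed one, the plan uses b/10,000, which can be zero. The form (b + 1)/(10,000 + 1) cannot. The two differ by at most 1/10,001, about 0.0001.

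**The case against.** The best defence is that the mismatch errs on the safe side. With no effect for any reader, the free shuffle rejected 1.5% to 4.1% of the time, so it creates no excess false positives there. The outcome is secondary. If readers and APL classes have similar concordance, the loss of power is negligible, and nothing in the documents shows that they differ much. All of this stands, and it limits the point.

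Three stronger readings are tempting, and the documents do not support them.

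- A reader might infer that the test loses substantial power. That holds only for strong differences between readers or APL classes, whose size the documents do not give.
- A reader might infer that a permuted data set could draw most of its AI-assisted reads from one clinician. It cannot: one reader supplies at most 68 of the 340 reads in a condition, or 20%.
- A reader might infer that stratifying the shuffle settles everything. It restores the match to the allocation, but it slightly raises the rejection rate when readers respond differently to the AI. It also gives exact p-values only if order and fatigue have no effect, because conditions are read in blocks (section 3.3) and section 9.5.1 lists fatigue as a risk.

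The defence leaves the claim of exactness unanswered. It also does not address inference beyond these 10 readers.

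**Conclusion.** The point holds, with limits. As written, section 7.3.3 does not give exact randomisation p-values, because its reference set is not the one that sections 3.4 and 5.1.2 generate. That much follows from the text without any assumption.

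The size of the consequence does rest on assumptions. The power cost runs from none to about 16 points, with 3 to 7 points for moderate to larger differences. The anti-conservatism for a claim about the average reader arises only if readers respond differently to the AI, and it is a separate defect with its own remedy. The figures for it depend on the assumed response SDs and include a small true shift in mean concordance. The primary analysis is not affected.

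**What to change.** In section 7.3.3, step 4, permute condition labels within each reader and within APL status, and compute p as (count + 1)/(10,000 + 1). Delete the statement that reads are independent. State that exactness assumes no order or fatigue effect.

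Base any claim about clinicians in general on the exact sign-flip test of the 10 within-reader differences in concordance, one for each pair of conditions. With 2^10 = 1,024 sign patterns, the smallest attainable two-sided p-value is 2/1,024, about 0.002, so the 0.05 level can be reached.

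The cost is a few lines of code and some SAP wording. The platform already records reader, slide and condition for each read (section 5.2.3), and APL status comes from the reference standard (section 3.8). The reader-level test has lower power than the read-level one, which is the price of generalising from 10 readers. Sections 5.3 and 10.2 show data collection complete, and section 10.3 records no amendments. The new tests should therefore be labelled as a change and reported beside the planned one.
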